4.1 Inclusion

1. Adult aged 18 and above

2. Diagnosis with major depressive disorder or reference to “clinical depression” in patient charts. See **Appendix 1** for ICD codes for major depressive disorders
3. Recently prescribed monotherapy antidepressant medication (defined as new start, medication switch, or dose change in the past 3 months (**Appendix 2**).
4. Patients with inadequate response or tolerability concerns determined based on A PHQ-2 score of 3 or greater, or a PHQ-2 <3 with a PHQ-9 score of 5 or greater recorded in medical records in the past 6 weeks or during screening,
5. Able and willing to provide informed consent
6. Able to use the Pathway Platform based on clinician’s judgment, e.g. owns an iPhone version 5 or later or smartphones with Android operating systems, have an active data plan or regular WiFi access.

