4.4.1 Pathway App

Pathway is a mobile application designed to gather health information related to the management of depression to enhance patient clinical engagement and guide patient care. The patient facing interface includes a digital assistant that allows patients to interact with the Pathway Platform in a chat-based conversational text interface. The information collected from the patient is intended to assist the care team in managing the patient's depression through enhancing measurement-based care and shared-decision making - enhancing patient-provider engagement and ultimately patient outcomes. The study will deploy the most recent iteration of the Pathway Platform. Earlier iterations were piloted in four primary care clinics.¹⁶ Feedback from this pilot was used to enhance Pathway Platform functionality. The current iteration of the Pathway Platform, which is the version that will be used in the implementation study described in this protocol, prompts patients to complete four scales to assess depression status biweekly (Patient Health Questionnaire [PHQ-9] and Perceived Deficits Questionnaire-Depression [PDQ-D5]), quality of life (World Health Organization- Five Well Being Index [WHO-5]), and cognition (Digit Symbol Substitution Test [DSST]).^{7,17,18,19} The Pathway Platform also includes a daily evening check-in with the patient to collect information on medication adherence and side effects. Patients reporting side effects related to sleep are prompted to complete the PROMIS Sleep Disturbance 6a and patients reporting side effects related to sexual dysfunction are prompted to complete the Arizona Sexual Experience Scale (ASEX).^{20,21} An optional functionality of the Pathway Platform is to set and track goals using the Goal Attainment approach adapted for depression during clinic visits with a healthcare provider.²² In addition, the Pathway Platform includes patient facing education for the patient on how to use the Pathway Platform to collect data as well as how to prepare for a visit with health care providers, set and assess progress towards goals and self-management. For purposes of evaluating this implementation study three additional scales assessing patient-provider engagement and functional improvement will be deployed through the Pathway Platform at baseline and subsequently every 6 months until the end of the study (Patient Activation Measure - 13[PAM-13], CollaboRATE, and Work and Social Adjustment Scale [WSAS]).^{23,24,25}

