4.4.2 Electronic Medical Record integration

Data collected in the Pathway Platform is electronically transmitted and stored in the patient's EMR. This data is accessible to the care team and provides a longitudinal summary that may assist in decision making and depression management. Providers can view this data either before or during the patient visit and use it to discuss future depression management.

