8.3 Outcomes

8.3.1 Primary outcome

The primary process outcome is PHQ-9 utilization over a six-month period. For purposes of this study, PHQ-9 utilization will be defined as documentation of at least 2 PHQ-9 scores in the EMR over the initial 6-month study period. The proportion of patients who meet this definition will be compared between patients attending clinics pre- and post- implementation of the Pathway Platform. Additional analyses exploring the number of PHQ-9s over the study period will also be conducted.

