8.3.3 Exploratory outcomes

Patient clinical and reported outcomes:

- The following patient reported outcomes will be collected in the Pathway Platform throughout the study. The difference in scores between the baseline measure, 6-months, and end of the study will be compared. This will be restricted to patients who completed these scales at these two-time points. To be inclusive of all patients, additional analyses will be conducted to compare first and last scores available:
 - PHQ-9
 - WHO-5
 - PDQ-D5

- The following patient reported outcomes will be collected in the Pathway Platform and described at 6-months and end of the study:
 - Antidepressant Medication adherence
 - Antidepressant Medication dose adjustment and switches
 - Side effects
 - Depression remission
 - Depression response
 - Goal attainment
- Patient reported outcomes (PAM-13, CollaboRATE and WSAS) will also be explored at 6 months and end of the study.

Pathway Platform and report utilization: Pathway Platform analytics will be explored to understand patient adherence to the platform which includes frequency of logging into the Pathway Platform and frequency of completing each of the Pathway Platform functionalities. Care-team utilization of Pathway Platform reports will also be explored, including describing type of care team members who viewed the Pathway Platform reports as well as frequency of viewing the reports.

Education utilization: Frequency of viewing material in the resource education center will be described by patient and by care-team members. Commonly viewed educational material will be highlighted.

Subgroup analysis: primary, secondary, and exploratory outcomes will be compared across a number of patient demographic and clinical characteristics, including PHQ-9 severity at baseline, comorbidities (see appendix 3 for comorbid conditions and ICD codes), app utilization by patients, and EMR report utilization by providers. Additional subgroup analysis will be conducted by type of care model at the site level (e.g. collaborative care vs. non collaborative care sites).

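### App utilization is partly made of the primary outcome and cannot be a subgroup factor for it; report utilization and baseline PHQ-9 severity need limits of their own

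*Combined protocol and SAP*

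**What the plan says.** The subgroup paragraph of section 8.3.3 states that "primary, secondary, and exploratory outcomes will be compared across a number of patient demographic and clinical characteristics, including PHQ-9 severity at baseline", then adds comorbidities and "app utilization by patients, and EMR report utilization by providers". The primary outcome is therefore expressly in scope for all of these factors. The same section measures patient adherence to the platform by log-in frequency and by "frequency of completing each of the Pathway Platform functionalities".

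Four other places bear on this:

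- Section 8.3.1 defines the primary outcome as "documentation of at least 2 PHQ-9 scores in the EMR over the initial 6-month study period". It does not exclude scores entered in the app.
- Section 4.4.1 says the app "prompts patients to complete four scales to assess depression status biweekly", and the PHQ-9 is one of the four. Section 4.4.2 says "Data collected in the Pathway Platform is electronically transmitted and stored in the patient's EMR".
- Section 4.1, criterion 4, admits patients on "A PHQ-2 score of 3 or greater, or a PHQ-2 <3 with a PHQ-9 score of 5 or greater". A PHQ-9 is not needed when the PHQ-2 is high enough, and exclusion 1 in section 4.2 names the two instruments jointly without clearly requiring the PHQ-9.
- Section 8.2 doubles the sample from 100 to 200 per group to allow for subgroup analyses, and section 8.4 applies p < 0.05 to all tests.

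The plan does not say whether a subgroup analysis is pre versus post within each level or within the post cohort only. It gives no cut-points for utilization and no rule for a missing factor value.

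**The concern.** A subgroup factor should be fixed before the outcome arises and be available in both groups compared. The three factors fall short of this to different degrees.

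- **App utilization** fails on both counts. The pre cohort never had the app, and completing app PHQ-9s is at once part of the factor and a route to the outcome.
- **Report utilization** by providers also arises after enrolment and only in the post cohort. Viewing a report is not part of the outcome definition, however.
- **Baseline PHQ-9 severity** is a legitimate baseline factor and is charted in both cohorts. It may be missing for pre patients who entered on PHQ-2 alone, and having a score may already supply one of the two that define success.

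At stake is interpretation. A significant difference by app use could be reported as evidence that engagement improves measurement-based care when it largely restates the definition. Shrunken effects within severity strata could be misread as a finding about who benefits.

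**Working it through.** **1. The plan's own figure.** For 75% against 90%, two-sided alpha 0.05 and 80% power (section 8.2), the pooled formula gives n = [1.960·√(2·0.825·0.175) + 0.842·√(0.75·0.25 + 0.90·0.10)]² / 0.15² = (1.053 + 0.443)² / 0.0225 ≈ 99.5, so 100 per group. This matches. Doubling to 200 cannot help app or report utilization, because neither factor has values in the pre cohort.

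**2. App utilization and the primary outcome.** Inputs: post rate 90% (section 8.2); h = share of post patients with two or more app PHQ-9s transmitted to the EMR (not stated; assumed 50% to 80%). Those patients succeed at 100% by definition. The rest must have rate (0.90 − h)/(1 − h), so the gap is 0.10/(1 − h). With 200 post patients, z = gap / √[0.9·0.1·(1/n₁ + 1/n₂)].

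| h | Rate in the rest | Gap | z |
|---|---|---|---|
| 50% | 80% | 20 points | 4.7 |
| 60% | 75% | 25 points | 5.8 |
| 70% | 67% | 33 points | 7.2 |
| 80% | 50% | 50 points | 9.4 |

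At h = 60% the rest sit at 75%, the planned pre rate. A 25-point difference by app use then appears with no change in charting for the patients without two app scores.

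**3. How far this depends on the metric.** Step 2 splits patients at two app PHQ-9s, but section 8.3.3 also counts log-ins and other functions. A simulation shows the range. Its assumptions are: clinics unchanged at 75%; 13 biweekly prompts (24/2 + 1); per-prompt completion varying between patients as Beta(1,3), Beta(1,1.5) or Beta(0.8,0.8); 200 post patients split at the median of the utilization measure.

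- Split on app PHQ-9 count: higher users reach 100%, the others about 84% to 92%. The chi-square test is significant in 94% to over 99% of trials.
- Split on a log-in measure correlated 0.3, 0.5 or 0.7 with PHQ-9 completion: gaps of about 3–4, 5–7 and 7–10 points, significant in roughly 14–19%, 35–42% and 70% of trials.

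The direction is the same throughout; the size depends on a metric that the plan does not fix.

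**4. Baseline PHQ-9 severity.** Let s be the share of pre patients with a baseline PHQ-9 and r the success rate among those without one (both assumed). With the overall pre rate at 75%, the rate among pre patients who can be placed in a stratum is (0.75 − (1 − s)·r)/s. The post rate is held at 90%.

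| s | r = 40%: pre rate, apparent effect | r = 60%: pre rate, apparent effect |
|---|---|---|
| 70% | 90%, 0 points | 81%, 9 points |
| 80% | 84%, 6 points | 79%, 11 points |
| 90% | 79%, 11 points | 77%, 13 points |
| 100% | 75%, 15 points | 75%, 15 points |

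An alternative model lets the baseline score count as one of the two and draws later PHQ-9s from a Poisson distribution, with the overall pre rate again fixed at 75%. It gives 12 points at 90% coverage, 6 at 70% and 2 at 50%. These are averages over strata; nothing here speaks to each stratum separately.

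**5. Report utilization.** No arithmetic applies. Opening a report does not add a PHQ-9 to the EMR. More visits or more app data could raise both report viewing and PHQ-9 counts, which is confounding within the post cohort.

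**The case against.** The strongest reply is that these analyses sit under exploratory outcomes, and that section 8.4 says exploratory outcomes are described among patients at platform clinics. That favours a post-only, descriptive reading of utilization. It does not settle the matter: the subgroup paragraph names the primary outcome, the sample was doubled for subgroup work, and a post-only comparison by app use is still circular.

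A reader might infer three stronger things that the documents do not support.

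- **That results for all three factors would be artefacts.** Report viewing is not a component of the outcome, and the Table 1 schedule lists PHQ-9 scores among the pre-implementation chart items, so severity is not confined to one cohort.
- **That heavy users are virtually certain to look significantly better.** This holds only if utilization is split on PHQ-9 completion itself; step 3 shows much weaker results for loosely related log-in measures.
- **That every severity stratum will show a smaller platform effect.** This needs incomplete PHQ-9 coverage before implementation, a qualifying score from up to six weeks earlier counting toward the two, and a lower success rate in patients without one. None of these is stated. App use is voluntary (section 7), so the post cohort may also lack some baseline scores. If 10% lack one and 60% of those succeed (assumed), the post rate within strata rises to (0.90 − 0.10·0.60)/0.90 = 93%, a partial offset.

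**Conclusion.** The point holds in graded form. For app utilization, comparing the primary outcome across use levels is largely circular by the plan's own definitions. The built-in gap is 20 to 50 points if 50% to 80% of post patients have two or more transmitted app scores and the post rate is 90%, and smaller where the utilization measure is only weakly tied to PHQ-9 completion. For report utilization, no pre-post subgroup contrast is possible, and a within-post comparison is confounded but not circular. For baseline PHQ-9 severity, the platform effect could be understated within strata; the planned 15 points might appear as anything from 0 to 13 at 70% to 90% coverage under the assumptions shown, with no distortion at full coverage. Coverage is not stated, so this part remains conditional. The comorbidity and care-model subgroups and the overall primary comparison are not affected by this issue.

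**What to change.** Amend the subgroup paragraph of section 8.3.3:

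1. Remove app utilization as a subgroup factor for the primary outcome and for the number of PHQ-9s.
2. For other outcomes, analyse app and report utilization in the post cohort only and report them as descriptive associations. Take app utilization from functions other than the PHQ-9, such as log-ins and daily check-ins.
3. Keep baseline PHQ-9 severity as a subgroup factor, defined in the same way in both cohorts, with a separate stratum for patients with no baseline PHQ-9 (PHQ-2 only), so that no patient is dropped.

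Replacing PHQ-9 severity by a PHQ-2 grade is not needed; it would be coarser, and the PHQ-2 is not an item in Table 1.

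The cost is plan wording, using items already scheduled for collection. The study gives up a primary-outcome result by app use and carries one extra severity stratum, which may be small.

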The primary objective of this study is to determine whether implementing the Pathway Platform in primary care improves adherence to measurement-based care practices.

Secondary objectives include determining whether implementing the Pathway Platform improves additional clinical process measures and depression response and remission outcomes.

Design and Outcomes

A pre- and post- study design is utilized to assess the impact of implementing the Pathway Platform in the primary care setting. Up to 20 primary care sites will be identified to participate in the study. Care team members involved in depression management will receive education on evidence-based clinical practices for depression care, such as measurement-based care practices and shared-decision making. Clinics with behavioral resources will also receive additional education on behavioral health integration. Training on how to onboard patients to use the Pathway Platform and utilize electronic medical records to view data collected in the Pathway Platform will also be provided. Study outcomes identified in this protocol will be assessed among 200 patients who will be enrolled in the Pathway Platform (post-implementation cohort). Outcomes will also be assessed in another 200 patients from the same participating clinics prior to study implementation (pre-implementation cohort). Implementation success will be evaluated by comparing study outcomes among the two cohorts with a total sample size of 400 patients (of which 200 will receive the intervention and 200 will not). The primary outcome is PHQ-9 utilization over six months and will be compared between the pre- and post- implementation cohorts. Additional process measures will be compared, including shared-decision making, medication adjustments, referrals to behavioral health, primary care follow-up post hospitalizations, and remission and response. Data collected in the Pathway Platform will also be evaluated to explore pre-defined patient outcomes. Additional outcomes will be explored in data captured from patients who continue to use the app beyond the initial 6 month study period.

Sample Size and Population

The study will take place in up to 20 primary care clinics within Advocate Aurora Health Care that are representative of different geographic locations, patient populations, and care models for

depression management, including behavioral health integration models.

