3.1 Performance among participating clinics post-implementation

The Pathway Platform will be implemented in up to 20 primary care sites within the Advocate Aurora Health system and enroll a total of 200 patients for six-month duration. The visit where the patient has been onboarded to the Pathway Platform will be the enrollment visit (Figure 1). During the post- implementation period, data on patient outcomes will be collected through the Pathway Platform. At the end of the study an electronic and manual chart review for patients using the Pathway Platform will be conducted among participating clinics and performance related to measurement-based care, shared decision making and collaborative care, where applicable, will be assessed over the post-implementation period.

3.2 Retrospective Assessment: pre-implementation performance at the clinic level (before Pathway Platform implementation)

To assess Advocate's primary care sites performance pre-implementation, an electronic and manual chart review will be conducted from the same Advocate primary care clinics participating in the implementation study. Patients with a clinic visit at least 6 months prior to implementation (index visit) of the Pathway Platform and meeting the inclusion criteria for enrollment in the study, will be included in this analysis (figure 1). Patient history will be evaluated for three months prior to index visit to confirm eligibility. The goal is to capture patients with a new start, dose adjustment or switch of an antidepressant medication 6 months prior to the implementation index date (three-month inclusion window for patient identification). Six months of patient history will be “retrospectively” collected for this baseline patient cohort to assess the primary outcome, defined as PHQ-9 utilization, and other secondary outcomes outlined in the protocol. This analysis will serve as the comparison control for the primary and secondary outcomes to compare performance at the same clinics pre and post-implementation of the Pathway Platform. Depending on the number of eligible patients identified per site (20 per site), group level matching for age and sex may be conducted. The primary endpoint will be the proportion of patients with at least 2 PHQ-9 scores.

Figure 1: Study schematic

* Primary and secondary outcomes will be evaluated at 6 months, data collected beyond 6 months will be used for exploratory analysis

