4.4.3 Educational Scaffolding

An online Educational training program was developed using evidence-based medicine building

on measurement-based care and shared-decision making concepts as they relate to depression management. Educational material describes how the Pathway Platform can help care team members in clinical processes related to these process improvement measures. In clinics using a collaborative care model additional education material specific to this care model is provided. Educational material housed in an online resource center which includes reading material, presentations, and videos. Additionally, up to three audit and feedback sessions will be conducted for each participating clinic. The objectives of audit and feedback sessions are to benchmark performance measures, including shared decision making, reflect on current clinical practice and improvement strategies, and setting team-based action plans. Care team members who manage depression must complete specific training before they are able to enroll patients and begin using the Pathway Platform.

A training manual was also developed for patients. The manual describes the Pathway Platform functionality, as well as, how to use and interpret the data collected.

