8.2 Sample size and randomization

The primary outcome for this study is PHQ-9 utilization. Assuming 75% PHQ-9 utilization prior to implementation of the Pathway Platform and 90% PHQ-9 utilization after implementation of the Pathway Platform, we will need 100 patients per group, for a total of 200 patients, assuming 80% power and a 2-sided alpha of 0.05 using Pearson chi square test for two independent proportions. To allow for subgroup analyses the sample will include 200 patients per group, for a total of 400 patients; 200 patients will comprise the “post-implementation” cohort and 200 will comprise the “pre-implementation” cohort. **Table 2** presents additional sample size calculations based on different assumptions of PHQ-9 utilization.

Table 2: Sample size calculations based on different assumptions of PHQ-9 utilization, alpha = 0.05, Power = 80%.
--

PHQ-9 utilization pre-implementation	PHQ-9 in Pathway post-implementation	N patients per group
75%	80%	1,094 per group
75%	90%	100 per group
75%	95%	49 per group
50%	65%	170 per group
50%	80%	30 per group
50%	90%	20 per group

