8.4 Data analysis

For primary and secondary hypothesis testing, process measures, patient clinical outcomes, and health care resource utilization will be compared pre- and post- implementation of the Pathway Platform.

Additional patient reported outcomes will be compared among patients using the Pathway Platform only at baseline and end of study. For pre-implementation, outcomes will be assessed among patients who visited one of the study clinics at least once over the pre-implementation study period and were eligible to use the Pathway Platform, if it had been available. For the post-implementation period, the Pathway Platform will be the data source for paired t-test analysis, assessing change in continuous variables including PHQ-9 scores. Categorical outcomes will be presented as proportions and compared using Pearson Chi2 test. Continuous outcomes will be assessed for normality and presented as means and standard deviations (SD) or medians and interquartile ranges (IQR); continuous outcomes will be compared using Student's t test for independent groups. Two-tailed tests using a significance threshold of $p < 0.05$ will be used for all tests.

Exploratory outcomes: will be described among patients attending the pathway platform clinics only and will be compared between baseline, 6-month and extended follow up. Change in these outcomes overtime, including utilization analytics will also be explored. Categorical outcomes will be presented as proportions and compared using McNemars' test. Continuous outcomes will be assessed for normality and presented as means and standard deviations (SD) or medians and interquartile ranges (IQR); continuous outcomes will be compared using Student's Paired t test for single group comparison. Two-tailed tests using a significance threshold of $p < 0.05$ will be used for all tests. Goal attainment will be summarized by proportion of patients who achieve their identified goals based on the set time bound duration of the goal (i.e., GAS Score ≥ 50).^{29,30} The goal attainment scale adapted for depression yields a norm-based score (standardized to a mean of 50, SD of 10) at baseline and at the end of the time bound goal; the change from score from baseline will also be summarized.

System level performance: Process outcomes will be evaluated at the system level (all primary

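### The care-model subgroup compares clinics, but every test the plan lists treats patients as independent; a direct comparison of care models needs the clinic as the unit

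*Combined protocol and SAP*

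**What the plan says.** The subgroup paragraph of Section 8.3.3 says that "primary, secondary, and exploratory outcomes will be compared across a number of patient demographic and clinical characteristics". It then adds: "Additional subgroup analysis will be conducted by type of care model at the site level", giving collaborative against non-collaborative care sites as the example.

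On the number of clinics, the synopsis says: "Up to 20 primary care sites will be identified to participate in the study". Section 8.2 finds 100 patients per group sufficient for the primary comparison and then enlarges the sample: "To allow for subgroup analyses the sample will include 200 patients per group, for a total of 400 patients".

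Section 8.4 gives the tests. For primary and secondary outcomes: "Categorical outcomes will be presented as proportions and compared using Pearson Chi2 test", with Student's t test for independent groups for continuous outcomes. For exploratory outcomes it names McNemar's test and the paired t test. All are two-sided at 0.05. Neither 8.2 nor 8.4 mentions an ICC, a design effect, a clinic effect, a cluster-robust variance or a clinic-level summary.

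Section 4.4.3 adds a difference between the two kinds of clinic: "In clinics using a collaborative care model additional education material specific to this care model is provided".

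**The concern.** All patients at one clinic share its care model, so the independent units in a care-model comparison are the clinics, at most 20 of them. Differences between clinics in staff, habits and case mix do not average out in a contrast between two sets of clinics. A chi-square or t test that counts patients as independent leaves that variation out of the standard error.

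Section 8.2 doubles the sample with subgroup analyses as the stated reason, and Section 4 sets out to include clinics with different care models. The result is therefore meant to be read. Under a patient-level test, ordinary variation between clinics could pass for an effect of care model.

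The meaning of the contrast is a second, smaller matter. Collaborative-care clinics also receive education specific to that model, so the comparison cannot separate the model from its training.

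**Working it through.** **1. Does the plan's own calculation allow for clinics?** Inputs from 8.2: 75% against 90%, 80% power, two-sided 0.05, Pearson chi-square. The pooled proportion is 0.825.

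n = [1.96·√(2·0.825·0.175) + 0.8416·√(0.75·0.25 + 0.90·0.10)]² / 0.15² = [1.96·0.5374 + 0.8416·0.5268]² / 0.0225 = 99.5, which rounds up to 100.

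This reproduces the stated 100 per group with no design effect.

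**2. Patients per clinic, m, within one cohort.** With 20 clinics, m = 200/20 = 10. Section 3.2 mentions a figure per site: "Depending on the number of eligible patients identified per site (20 per site), group level matching for age and sex may be conducted". If that means 20 per cohort, there are 200/20 = 10 clinics and m = 20. If it means both cohorts together, there are 400/20 = 20 clinics and m = 10 per cohort. Both cases are shown.

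**3. Direct comparison of care models in one cohort.** The ICC is an assumption, 0.01 to 0.10. With clinics of equal size:

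Design effect DE = 1 + (m − 1)·ICC; actual false-positive rate = 2·[1 − Φ(1.96/√DE)].

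| ICC (assumed) | DE, m = 10 | Rate, 20 clinics | DE, m = 20 | Rate, 10 clinics |
|---|---|---|---|---|
| 0.01 | 1.09 | 6.1% | 1.19 | 7.2% |
| 0.02 | 1.18 | 7.1% | 1.38 | 9.5% |
| 0.05 | 1.45 | 10.4% | 1.95 | 16.0% |
| 0.10 | 1.90 | 15.5% | 2.90 | 25.0% |

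Example for m = 10, ICC 0.05: 1.96/√1.45 = 1.628, and 2·[1 − Φ(1.628)] = 10.4%.

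Beta-binomial simulation (40,000 runs per setting; true rates 50%, 75% and 90%; even and uneven splits of clinics) agrees closely. With 10 clinics, m = 20 and ICC 0.10, for example, the patient-level test rejects in 22.5% to 26.9% of runs. A t test on clinic proportions rejects in 4.0% to 5.3% across all settings.

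**4. Cohort-by-care-model contrast.** Both cohorts come from the same clinics, so a stable clinic effect subtracts out. Simulated rates for the patient-level interaction test, normal outcome:

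| ICC (assumed) | 20 clinics, stable effects | 20 clinics, half the clinic variance changes | 10 clinics, stable effects | 10 clinics, half the clinic variance changes |
|---|---|---|---|---|
| 0.01 | 4.9% | 5.5% | 4.9% | 5.9% |
| 0.02 | 4.8% | 6.1% | 4.7% | 7.0% |
| 0.05 | 4.3% | 7.4% | 4.3% | 10.5% |
| 0.10 | 3.9% | 9.6% | 4.0% | 15.3% |

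A pre/post test within one care model behaves the same way, with a maximum of 15.7%.

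**5. Which outcomes have no pre-period?** App use, care-team report viewing, goal attainment, and changes in PAM-13, CollaboRATE, WSAS, WHO-5 and PDQ-D5 exist only after implementation. For these, care models can only be compared clinic against clinic, so the table in step 3 applies. Subtracting a patient's own baseline does not remove clinic differences in the amount of change. McNemar's test and the paired t test compare a patient with himself or herself over time and cannot compare two sets of clinics.

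**The case against.** Several stronger readings are tempting, and the documents do not support them.

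- A reader might infer that 8.4 prescribes a wrong test for this subgroup. It assigns none. The chi-square and independent t tests stand in the paragraph on primary and secondary outcomes. The reference to the site level could describe the factor or an intended site-level analysis. Patient-level testing is an inference from the only tests listed. This stands, although no site-level method appears anywhere in the plan.
- A reader might infer that the error rate is far above 5%. No ICC is given. With 20 clinics and an ICC of 0.01–0.02 the rate is 6–7%; it reaches double the nominal level only near 0.05. The 25% figure also needs 10 clinics.
- A reader might carry those rates over to the statement that the Platform works better in collaborative-care clinics. For outcomes measured in both cohorts, that statement is a difference in pre/post change, in which stable clinic effects cancel. This is right, subject to stability. Section 4.4.3 provides up to three audit-and-feedback sessions per clinic, with team action plans, so change could well differ between clinics.
- A reader might suppose that the subgroup result decides roll-out. No passage says so. The analysis is exploratory, and care model is not among the objectives.

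The extra education is openly described, so the point there is one of labelling, separate from the standard error.

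These objections limit the size and reach of the problem. They do not answer it for outcomes seen only in the Platform cohort.

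**Conclusion.** The point holds in a limited form. The plan intends to compare outcomes by a clinic-level factor and offers no method that allows for clinic. A direct patient-level comparison of care models exceeds its nominal 5% for any positive ICC: about 6–16% with 20 clinics of 10 patients and 7–25% with 10 clinics of 20. For the pre/post-by-care-model contrast there is little or no inflation under stable clinic effects. If half the clinic variance changes between periods, the rate is about 5.5–9.6% with 20 clinics and 5.9–15.3% with 10.

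These figures rest on assumed ICCs, equal clinic sizes and, for step 4, an assumed share of clinic variance that changes. None of these is in the documents, and neither is the split of clinics by care model. The direction of the error in a direct comparison does not depend on them. The primary pre/post test is not affected by this point.

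**What to change.** In 8.3.3 and 8.4:

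- State that care-model comparisons take the clinic as the unit: a t test on clinic means or proportions, or a mixed model with a clinic random effect and small-sample degrees of freedom. The t test on clinic proportions is the simpler default and held its level in the simulations.
- For outcomes measured in both cohorts, use the cohort-by-care-model term with clinic effects allowed to differ by period, or a t test on each clinic's pre/post change.
- Report the number of clinics in each care model.
- Describe the contrast as care model together with its model-specific education.

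The cost is a change of wording; patients are identified by participating clinic, so no new data are needed. The interval for this subgroup widens. At an assumed ICC of 0.05, a direct comparison with 20 clinics (18 degrees of freedom, t = 2.10) has an interval √1.45 × 2.10/1.96 = 1.29 times as wide. With 10 clinics (8 degrees of freedom, t = 2.31) the factor is √1.95 × 2.31/1.96 = 1.65.
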